9.4.3. Laboratory Tests

For each patient, laboratory tests detailed in Appendix 2 should be conducted according to the Schedule of Activities (Section 2).

Any clinically significant findings from laboratory tests that result in a diagnosis and that occur after the patient receives the first dose of investigational product should be reported to Lilly or its designee as an AE.

9.4.4. Safety Monitoring

Lilly will periodically review evolving aggregate safety data within the study by appropriate methods. In addition, the study team will review safety reports in a blinded fashion according to the schedule provided in the Trial-Level Safety Review plan. Lilly will also review SAEs within time frames mandated by company procedures. The Lilly CRP/CRS will, as appropriate, consult with the functionally independent Global Patient Safety therapeutic area physician or clinical scientist.

In addition, specific safety measures are included in the protocol to ensure appropriate monitoring of pancreatic, thyroid, and liver safety. Laboratory findings that trigger pancreatic and thyroid safety monitoring per Lilly standards are provided in Sections 9.2.1.2.5 and 9.2.1.2.7, respectively. Details of liver safety monitoring are provided in Section 8.1.1. If a study patient experiences elevated ALT $\geq 3 \times$ ULN or elevated total bilirubin $\geq 2 \times$ ULN, clinical and laboratory monitoring should be initiated by the investigator. Details for hepatic monitoring depend upon the severity and persistence of observed laboratory test abnormalities. To ensure patient safety and comply with regulatory guidance, the investigator is to consult with the Lilly CRP/CRS regarding collection of specific recommended clinical information and follow-up laboratory tests (see Appendix 4).

9.5. Pharmacokinetics

Blood samples for PK analyses will be collected from all randomized patients in accordance with the Schedule of Activities (Section 2) and at ET. However, only samples from patients assigned to treatment with LY3298176 will be analyzed for drug concentration.

Date and time of each sample and the most recent LY3298176 dose prior to PK blood draw must be recorded. Scheduled PK samples must be collected prior to dose administration at scheduled visits.

Drug concentration information that would unblind the study will not be reported to study sites or blinded personnel while the study is blinded.

Bioanalytical samples collected to measure study drug concentration will be retained for a maximum of 1 year following the last patient visit for the study.

9.6. Pharmacodynamics

Samples to evaluate the PD properties of LY3298176 are included in the secondary efficacy measures and not applicable here.

9.7. Pharmacogenomics

Not applicable.

9.8. Biomarkers

Collection of samples for other biomarker research is part of this study. Blood samples will be collected as specified in Section 2.

Biomarker research is performed to address questions of relevance to drug disposition, target engagement, PD, mechanism of action, variability of patient response (including safety), and clinical outcome. Sample collection is incorporated into clinical studies to enable examination of these questions through measurements of biomolecules, including DNA, RNA, proteins, lipids, and other cellular elements.

Serum and plasma ethylenediaminetetraacetic acid (EDTA) samples for nonpharmacogenetic biomarker research will be collected at the times specified in the Schedule of Activities (Section 2) where local regulations allow.

Samples will be used for research on the drug target, disease process, variable response to LY3298176, pathways associated with diabetes, mechanism of action of LY3298176, and/or research method or in validating diagnostic tools or assay(s) related to diabetes.

Samples will be retained for a maximum of 15 years after the last patient visit for the study, or for a shorter period if local regulations and ERBs impose shorter time limits, at a facility selected by Lilly. This retention period enables use of new technologies, response to regulatory questions, and investigation of variable response that may not be observed until later in the development of LY3298176 or after LY3298176 becomes commercially available.

9.9. Health Economics

Not applicable.

9.10. Samples for Immunogenicity Research

Samples from all patients will be tested for antidrug antibodies (ADA) against LY3298176. A blood sample will be collected at specific study visits according to the Schedule of Activities (Section 2). All samples for immunogenicity should be taken predose when applicable. To interpret the results of immunogenicity, a PK sample should be collected at the same time point as an the immunogenicity sample. In the event of drug hypersensitivity reactions (immediate or nonimmediate), additional samples will be collected as close to the onset of the event as possible, at the resolution of the event, and 30 days following the event. Instructions for the collection and handling of blood samples will be provided by the sponsor. The actual date and 24-hour clock time of each sampling will be recorded.

Immunogenicity will be assessed using a validated ligand-binding assay designed to detect and titer ADA in the presence of LY3298176 at a laboratory approved by the sponsor. Confirmed positive samples for LY3298176 ADA will be titrated and then evaluated for cross-reactive binding to native GIP and GLP-1 using a validated ligand-binding assay. They may also be tested for their ability to neutralize the activity of assigned treatment (LY3298176-neutralizing antibodies) in separate cell-based neutralizing assays over-expressing the GIP and GLP-1 receptors. Antidrug antibody samples that test positive for neutralizing activity against LY3298176 and/or for cross-reactive binding to native GIP and GLP-1 may then be further tested for neutralizing activity against native GLP-1 and GIP using cell-based neutralizing assays.

All patients will have an ADA sample measured at ET or at the follow-up visit (Visit 801) approximately 1 month after the last dose of LY3298176. A risk-based approach will be used to monitor patients who have clinically significant treatment-emergent antidrug antibodies (TE-ADA) at the last visit. Treatment-emergent ADA are defined as those with a titer 2-fold (1 dilution) greater than the minimum required dilution if no ADA were detected at baseline or those with a 4-fold (2 dilutions) increase in titer compared to baseline if ADA were detected at baseline. Clinically significant TE-ADA will be defined as any TE-ADA at the follow-up visit (Visit 801) with:

- A high titer (≥ 1280) or an increasing titer from last measured value
- An association of TE-ADA with a moderate to severe injection site reaction or infusion-related reaction
- Cross-reactive and/or neutralizing binding of an ADA with endogenous GLP-1 or GIP.

Patients who have clinically significant TE-ADA should be followed with ADA testing every 3 months for approximately 1 year or until the ADA titers have returned to baseline ADA titer (defined as ADA titer within 2-fold of baseline). A PK sample may be collected at the follow-up immunogenicity assessment(s) if warranted and agreed upon between both the investigator and sponsor.

Every attempt should be made to contact patients for the follow-up immunogenicity assessment; however, if patients are unwilling or unable to return for the visit, this is not considered a protocol violation.

Patients followed for at least 1 year since last dose who have not returned to baseline, as defined above, will be assessed for safety concerns and, if no clinical sequelae is recognized by the clinical team, no further follow-up will be required.

Patients who have clinical sequelae that are considered potentially related to the presence of TE-ADA may also be asked to return for additional follow-up testing.

Samples will be retained for a maximum of 15 years after the last patient visit for the study, or for a shorter period if regulations and ERBs impose shorter time limits, at a facility selected by Lilly. The duration allows the sponsor to respond to future regulatory requests related to LY3298176. Any samples remaining after 15 years will be destroyed.

10. Statistical Considerations

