- h Collect serum FSH in women whose menopausal status needs to be determined.

- i The patients should collect the SMBG during the lead-in period between Visits 2 and 3 and return the results within their diaries at Visit 3.
- j The patients should collect the SMBG during the week after Dose 12 and return the results within their diaries at Visit 10.
- k PK samples are to be collected pre-dose.
- l Patients who have clinically significant TE-ADA should be followed with ADA testing every 3 months for approximately 1 year or until the ADA titers have returned to baseline ADA titer (defined as ADA titer within 2-fold of baseline). Patients who have clinical sequelae that are considered potentially related to the presence of TE-ADA may also be asked to return for additional follow-up testing.

3. Introduction

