Patients who develop severe, persistent hyperglycemia based on prespecified thresholds (see Section [9.2.1.2.4](#)) will receive a new glucose-lowering intervention (or rescue therapy) based on clinical judgment of the investigator, and the patient will discontinue study drug. Patients who need rescue therapy for this reason will be asked to remain in the trial until they complete all study visits for collection of safety information. Patients who discontinue study drug due to AEs will also be asked to continue in the trial for collection of safety information. Patients who are unable or unwilling to continue in the study because of an AE or any other reason will perform

an early termination (ET) visit as their final study visit. If the patient is discontinuing during an unscheduled visit, that visit should be performed as the ET visit. If the patient is discontinuing during a scheduled visit, that visit should be considered the ET visit. At this visit, patients will perform procedures listed in the Schedule of Activities (Section 2).

Study Period III (Safety Follow-Up, Visit 801):

All randomized patients who complete the treatment period will complete the safety follow-up approximately 4 weeks after their last visit on treatment.

Patients randomized to LY3298176 who have treatment-emergent anti-LY3298176 antibodies or antibodies to native GIP or GLP-1 at the last visit may be monitored after the last visit (see Section 9.9).

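### Protocol Section 9.10 defines clinically significant TE-ADA at Visit 801 only, so patients whose last ADA sample is at early termination fall outside the definition that triggers the scheduled 3-monthly antibody testing

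*Protocol*

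**What the plan says.** Three statements in Protocol Section 9.10 bear on this, close together in the same paragraph.

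- On the closing sample: "All patients will have an ADA sample measured at ET or at the follow-up visit (Visit 801").
- On who is monitored: "A risk-based approach will be used to monitor patients who have clinically significant treatment-emergent antidrug antibodies (TE-ADA) at the last visit".
- On the definition: "Clinically significant TE-ADA will be defined as any TE-ADA at the follow-up visit (Visit 801) with" a high or rising titer, an association with a moderate to severe injection site or infusion-related reaction, or cross-reactive or neutralizing binding to endogenous GLP-1 or GIP.

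The scheduled follow-up depends on that definition. Both Section 9.10 and footnote l of the Schedule of Activities (Table GPGF.1) say: "Patients who have clinically significant TE-ADA should be followed with ADA testing every 3 months for approximately 1 year", or until the titer is back to baseline. SAP Appendix 1 repeats the footnote.

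Protocol Section 5.1 separates the two closing visits. Patients unable or unwilling to continue have "an early termination (ET) visit as their final study visit". For the safety follow-up (Visit 801) it says: "All randomized patients who complete the treatment period will complete the safety follow-up approximately 4 weeks after their last visit on treatment".

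**The concern.** The first two statements in Section 9.10 include patients whose last visit is ET. The definition that follows names Visit 801 alone. A patient who leaves at ET has no Visit 801 sample, so the ET sample is drawn and tested but cannot make the patient's TE-ADA clinically significant as defined. This holds even with a titer of 1280 or more, or with antibodies that cross-react with native GLP-1 or GIP.

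What is at stake is safety follow-up. A group that the paragraph appears to mean to monitor drops out of the scheduled testing when the rule is followed as written. Sites may also act differently, depending on which sentence they follow.

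**Working it through.** **Setting the texts side by side**

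| Element | Visit named | Includes a patient who leaves at ET? |
|---|---|---|
| Closing ADA sample (9.10) | ET or Visit 801 | Yes |
| Risk-based monitoring (9.10) | Last visit | Yes |
| Definition of clinically significant TE-ADA (9.10) | Visit 801 | No |
| 3-monthly ADA testing (9.10; Table GPGF.1 footnote l) | None, but uses the defined term | No, through the definition |
| Discretionary monitoring (5.1, Study Period III) | Last visit | Yes, but optional |
| Return for clinical sequelae (9.10; footnote l) | None | Yes, but optional |
| Extra samples after a hypersensitivity reaction (9.10) | Onset, resolution, 30 days after | Yes, if such an event occurs |

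The third row conflicts with the first two, and the fourth inherits the conflict. The discretionary sentence in Section 5.1 sends the reader to Section 9.9, which is Health Economics and marked not applicable. The immunogenicity rules are in Section 9.10.

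**Size of the group**

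Inputs: about 20 completers per arm and 13% dropout (Protocol Section 10.1); four arms at 1:1:1:1 (Section 5.1).

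1. Reproduce the plan's total: 20 / (1 − 0.13) = 22.99, rounded up to 23 per arm; 23 × 4 = 92. This matches the protocol.
2. Planned dropouts: 92 × 0.13 = 11.96, about 12. The same follows from 92 − 80 = 12.
3. On LY3298176: 3 × 23 = 69; 69 × 0.13 = 8.97, about 9.

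These are upper ends at the planned dropout rate. They assume that every dropout leaves the study and attends an ET visit. Some may be lost to follow-up with no ET sample (Section 8.3), so the range is 0 to about 12 overall and 0 to about 9 on LY3298176. Only those with TE-ADA and a listed feature would be affected, and neither document gives a TE-ADA rate from which to reduce the range further.

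**Effect on the planned analysis**

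SAP Section 6.11.2.3 classifies a patient as TE-ADA positive from any qualifying postbaseline sample. Section 6.11.2.4 tabulates this for the active treatment period and for the whole postbaseline period. The ET sample counts there, and the clinically significant category is not used. The incidence result does not change.

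**The case against.** The strongest reply is that this is a wording slip with other safeguards around it. Much of that stands.

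- A reader might infer that patients who leave at ET can never receive antibody follow-up. The documents do not support that. Section 5.1 allows monitoring of LY3298176 patients with treatment-emergent antibodies at the last visit. Section 9.10 adds: "Patients who have clinical sequelae that are considered potentially related to the presence of TE-ADA may also be asked to return". Hypersensitivity reactions trigger extra samples, and Section 9.2 requires follow-up of serious, related or discontinuation-causing adverse events. What is lost is the scheduled 3-monthly testing. The discretionary routes do not replace it: one is optional and points to the wrong section, and the other needs clinical sequelae, which a high titer alone does not supply.
- A reader might take 12 of 92 as the number affected. It is an upper end. Patients who stop study drug are asked to stay in the study (Sections 5.1 and 8.1.1) and can still reach Visit 801. Section 5.1 says that treatment completers attend Visit 801; it does not say that nobody else may.
- A reader might suppose that early leavers left mostly because of reactions. Nothing in the documents shows this.
- A reader might think that the secondary endpoint of antibody incidence is harmed. It is not, for the reason given in the working. No persistence analysis is planned either.
- The position of footnote l, on the Visit 801 immunogenicity cell and not on the ET cell, is weak evidence. Superscripts in the extracted tables are unreliable, and the footnote's text names no visit. The point rests on the wording of Section 9.10.

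None of this removes the contradiction within Section 9.10.

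**Conclusion.** The point holds as an internal inconsistency in a safety follow-up rule. Section 9.10 collects the closing sample at ET or Visit 801 and monitors by the last visit, yet defines clinically significant TE-ADA at Visit 801 alone. Patients whose final visit is ET therefore fall outside the trigger for scheduled ADA testing. That the section means ET patients to be covered is a fair inference from the two preceding statements; no single sentence says so.

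The consequence is confined to follow-up of a small group, possibly nobody. It rests on a literal reading of the definition and on ET being the last contact for patients who leave the study. No planned estimate or test changes.

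**What to change.** The sponsor should:

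1. Reconcile the Visit 801 definition in Protocol Section 9.10 with the closing-sample and last-visit statements before it, and state explicitly whether patients whose last sample is at ET are covered. That decision is the sponsor's.
2. Align footnote l, and the cells that carry it, in Table GPGF.1 and SAP Appendix 1 with the decision.
3. Correct the reference to Section 9.9 in Section 5.1 (Study Period III), since the immunogenicity rules are in Section 9.10.

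The cost is a wording change in both documents. If ET patients are covered, a few extra ADA draws may follow, limited to those who meet the listed features. No analysis needs to change.

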10.1. Sample Size Determination

Approximately 92 patients will be randomized to placebo or 1 of 3 LY3298176 titrations arms assuming a 13% dropout rate resulting in approximately 20 completers per arm.

Assuming a standard deviation of 1.1, 20 patients per arm will provide at least 90% power to detect a statistically significant difference between LY treatments to placebo with a dose response assumption as shown in [Table GPGF.4](#).

Table GPGF.4. Dose–Response Assumption Used in Sample Size Determination

	Placebo	LY 12 mg	LY 15 mg-1	LY 15 mg-2
CFBL HbA1c (%)	-0.2%	-1.4%	-1.5%	-1.5%

Abbreviations: CFBL = change from baseline; LY = LY3298176.

10.2. Populations for Analyses

For purposes of analysis, the following populations are defined in [Table GPGF.5](#).

Table GPGF.5. Definitions of Populations to Be Analyzed in Study GPGF

Population	Description
Enrolled	All participants who sign informed consent.
ITT (intention-to-treat)	All randomized patients.
mITT (modified ITT)	All randomized patients with at least 1 postbaseline measurement according to the treatment the patients were assigned.
PP (per-protocol)	All randomized patients who were compliant with study drug and completed the protocol.
Safety	All randomized participants who take at least 1 dose of study treatment. Participants will be included in the treatment group to which they were randomized. In the event of a treatment error, participants will be analyzed according to the treatment they actually received.

10.3. Statistical Analyses

10.3.1. General Statistical Considerations

Statistical analysis of this study will be the responsibility of Lilly or its designee. Any change to the statistical methods described in the protocol will require an amendment only if it changes a principal feature of the protocol. Any other change to the statistical analyses and the justification for the change will be described in the statistical analysis plan (SAP) and/or clinical study report (CSR). Additional exploratory analyses of the data may be performed as deemed appropriate. Analyses will be fully detailed in the SAP.

The intention-to-treat (ITT) population is defined as all randomized patients. Statistical analyses (including the primary analysis) will be conducted on the modified ITT (mITT) population. The mITT population is defined as all randomized patients with at least 1 postbaseline measurement according to the treatment the patients were assigned. The per-protocol (PP) population is defined as all randomized patients who were compliant with study drug and completed the

protocol and is a subset of the mITT population. The safety population is defined as all randomized patients who have received at least 1 dose of study drug. Safety analyses will be performed on the safety population.

Some efficacy measures will also be analyzed on the PP dataset. The PP analysis will include patients who meet the following additional criteria:

- Have been appropriately randomized
- Have not discontinued from the study for any of the early discontinuation criteria
- Have not missed ≥ 2 doses during the treatment period
- Have not been rescued or taken a concomitant antihyperglycemic medication besides metformin for >7 cumulative days during the treatment period.

Patients who have had rescue therapy will be included in the mITT population, but not the PP population. The efficacy measures will be censored at the time of rescue for analyses using mITT population.

No adjustments for multiplicity will be performed.

All tests of treatment effects will be conducted at a one-sided alpha level of 0.1 and/or one-sided 90% confidence interval, unless otherwise stated.

The baseline value used for the analyses will be the last scheduled baseline value obtained for each patient prior to randomization.

10.3.2. Treatment Group Comparability

10.3.2.1. Patient Disposition

All patients who discontinue the study will be identified, and the extent of their participation in the study will be reported. If known, a reason for their discontinuation will be given. The primary reasons for discontinuation will be listed and will be summarized by treatment. The percentage of patients discontinuing from each treatment will be compared using the Fisher's exact test.

10.3.2.2. Patient Characteristics

Demographic and baseline characteristics will be summarized by treatment group. Categorical variables will be summarized by frequencies and percentages. For categorical variables, comparisons between treatment groups will be assessed using a Pearson Chi-Square test. Continuous variables will be summarized by means and SDs. For continuous variables, comparisons between the treatment groups will be performed using a 1-way analysis of variance with treatment as the fixed effect.

10.3.2.3. Concomitant Therapy

Listings and summary of concomitant therapies will be provided by treatment group.

10.3.2.4. Treatment Compliance

Treatment compliance will be listed using all randomized patients and summarized using the mITT population. For a given patient, overall compliance for treatment period is defined as not

missing ≥ 2 doses of the assigned treatment at any point in the study. Patients who miss ≥ 2 doses at any point during the study will be considered significantly noncompliant and will be permanently discontinued from study medication. These patients will not be included in the PP analysis.

10.3.3. Efficacy Analyses

10.3.3.1. Primary Analyses

The primary outcome is the difference in HbA1c change from baseline between treatment groups based on the mITT population at the planned end of the treatment period of 3 months. The primary analysis model will be a mixed model for repeated measures (MMRM) for HbA1c change from baseline to 3 months in the mITT population with treatment, visit, treatment-by-visit, baseline BMI category, and metformin use (yes, no) as fixed effects, and baseline HbA1c as a covariate. The dependent variable will be the postbaseline change from baseline values. An unstructured covariance structure will be used to model the within-patient errors. If this model fails to converge, the following covariance structures will be tested in order:

- toeplitz with heterogeneity
- autoregressive with heterogeneity, by visit
- compound symmetry with heterogeneous variances by visit
- toeplitz
- autoregressive
- compound symmetry without heterogeneous variances, by visit
- compound symmetry.

The first covariance structure that converges will be used.

The treatment p-value will be used as evidence of difference between active drug and placebo, while the comparison of least-squares (LS) means versus placebo (unadjusted for multiple comparisons) will provide magnitude and significance of this difference. The primary analysis model, MMRM, will be repeated using the PP population. If the conclusion differs from that of the mITT population, the data and analyses will be further investigated.

Descriptive statistics by treatment for HbA1c and HbA1c change from baseline at the 12-week endpoint will be presented using all observed data with no imputations and no elimination of patients with protocol violations. The descriptive statistics will be presented by visit and will include sample size, mean, SD, median, minimum, and maximum.

